## Introduction

Puerperal mastitis is one of the most commonly reported problems during breastfeeding (1-3). Women frequently report breast pain, tenderness, redness, engorgement, fever, malaise, chills, lethargy, sweating, headache, nipple damage and a hot spot on the affected breast (4-6). These highly distressing symptoms may severely impact on a woman's daily activities and quality of life and might lead to the premature cessation of exclusive breastfeeding, which may have significant impact on infant health and survival.

The role of physical therapy in reducing pregnancy/postpartum-related disorders including breast problems is gaining momentum and importance in obstetrics (7). However, to date, only low-level evidence has shown positive effects of breast massage, a physical technique, on pain, milk supply and symptom relief in women with breastfeeding problems (7). This is encouraging, however further research is needed to explore whether physical therapy is effective to reduce symptoms of

puerperal mastitis. Therefore, the aims of this study were to explore clinical effects of therapeutic ultrasound, education and massage on mastitis symptoms and to compare the effectiveness of therapeutic ultrasound, education and massage versus usual obstetric care and sham ultrasound treatment on patient-centered outcomes in the short- and medium-term.

## Methods

A randomized controlled trial was conducted from May 2021 to April 2023. Postpartum lactating women aged from 21 to 45 with breast symptoms were recruited through the Obstetrics and Gynecology Clinic of National Cheng Kung University Hospital, the postpartum care centers, websites and community. Eligible participants were randomly allocated to the ultrasound group, sham group, or usual care group. Participants allocated to the ‘Ultrasound’ arm of the trial participated in four one-hour treatment sessions with the physical therapist over one week. The treatment included educating the patient about mastitis and self-management strategies, treating with therapeutic ultrasound and administering and teaching breast massage. Participants allocated to the ‘Sham’ group received the same education and breast massage sessions as described above. In addition, the sham control group received 5 minutes of ‘sham’ ultrasound at 0 W/cm^2 intensity from a physical therapist. Participants

allocated to the ‘Usual care’ group received usual obstetric care, which included verbal advice/printed patient information regarding mastitis and breastfeeding from the medical or nursing staff. The outcome measures including severity of breast symptoms (breast and nipple pain, breast engorgement), breast hardness, body temperature, breast temperature, breastfeeding self-efficacy, and milk volume were assessed at baseline, immediately post-intervention, and at 3 months following baseline. The acceptability of the intervention program and adverse events were recorded immediately post-intervention and at 3 months following baseline.

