#### Statistical analysis plan

The data were analyzed using intention-to-treat principles with the SPSS version 20.0 for Windows. The last observation carried forward imputation was used for imputing missing data. Descriptive statistics were used to summarize and report data. All outcome data were assessed for normality using the Kolmogorov-Smirnov test. Repeated measures analysis of variance with Bonferroni post hoc comparisons was used to compare changes in outcome variables between groups. The equivalent non-parametric tests (i.e. Friedman test and Kruskal Wallis test) were used if data were not normally distributed. Numbers, percentages, mean, standard deviation, median, interquartile range, and p-values were reported. All analyses were tested with a

significance level of  $p<0.05$ .

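### Each symptom is compared as unadjusted change in all randomised women, though entry requires no particular symptom; adjust for baseline and show the women who had the symptom alongside

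*Combined protocol and SAP*

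**What the plan says.** On entry, the Methods section states: "Postpartum lactating women aged from 21 to 45 with breast symptoms were recruited". No symptom is required and no minimum severity is given. The Introduction lists a wide range of complaints ("Women frequently report breast pain, tenderness, redness, engorgement, fever, malaise, chills, lethargy, sweating, headache, nipple damage and a hot spot on the affected breast") and does not say that they occur together.

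The outcomes in the Methods section are "severity of breast symptoms (breast and nipple pain, breast engorgement), breast hardness, body temperature, breast temperature, breastfeeding self-efficacy, and milk volume", measured at baseline, immediately after the intervention and at 3 months.

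The statistical analysis plan states: "The data were analyzed using intention-to-treat principles", and "Repeated measures analysis of variance with Bonferroni post hoc comparisons was used to compare changes in outcome variables between groups". If the data are not normal: "The equivalent non-parametric tests (i.e. Friedman test and Kruskal Wallis test) were used if data were not normally distributed". It names no baseline covariate, no analysis in women who had the symptom at entry, and no composite or worst-symptom score.

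**The concern.** As written, a woman could qualify with one complaint and score zero on the others. On an outcome where she starts at the floor she cannot improve in any arm, so she contributes little or nothing to the difference in relief. The all-women difference for that symptom then depends partly on how many recruits had it.

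Two things are at stake. First, the Introduction asks whether physical therapy reduces symptoms. A small or null difference on one symptom could mean that treatment does not relieve it, or that few women had it, and the planned output would not separate the two. Second, an unadjusted comparison of changes treats the gap between women who can change and women who cannot as noise. This arises outcome by outcome and does not depend on whether a woman has mastitis.

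**Working it through.** **Inputs.** From the documents: three arms, two follow-up visits, significance level 0.05. The documents state no sample size, effect size, SD, scale or symptom prevalence, so there is no planned figure to reproduce. Everything below is illustrative. Two-sided tests and equal arms are assumed.

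**1. Dilution.** Let q be the share with the symptom at baseline and d the effect in those women. If symptom-free women stay at the floor, the all-women effect is q × d, that is 90%, 70% or 50% of d at q = 0.9, 0.7 or 0.5. If treatment also prevents new symptoms, with effect r × d in symptom-free women, the share kept is q + (1 − q)r. At q = 0.7, r = 0.25 gives 0.7 + 0.3 × 0.25 = 0.775, and r = 0.5 gives 0.85.

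**2. Sample size.** Per arm, n = 2(1.960 + 0.842)² × SD² / effect² for 80% power.
- All symptomatic, d = 0.5 SD: 2 × 7.85 / 0.25, so 63.
- q = 0.7: the effect is 0.35. The variance is 0.7 if only the floor acts, 1 if unchanged, or 0.7 + 0.7 × 0.3 × 1.5² = 1.1725 if symptomatic women improve by 1.5 SD on average. This gives 90, 129 or 151.
- q = 0.9: 70 to 86. q = 0.5: 126 to 267.
- With 63 per arm, power is 67–76%, 44–65% and 28–51% at q = 0.9, 0.7 and 0.5.

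**3. Simulation on a symptom score.** Assumed: two arms of 30; a 0–10 score floored at 0; baseline mean 6 (SD 1.5) in symptomatic women; change = −0.5 × baseline + effect + noise; nominal effect −1.5; residual SD 2; symptom-free women stay at 0.

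| Share symptomatic | Difference, all women | Difference, symptomatic | Power, change, all | Power, change, symptomatic | Power, baseline-adjusted, all |
|---|---|---|---|---|---|
| 40% | -0.50 | -1.27 | 13% | 33% | 37% |
| 60% | -0.76 | -1.28 | 22% | 48% | 55% |
| 80% | -1.02 | -1.28 | 39% | 60% | 69% |

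The all-women differences agree with q × d: 0.6 × -1.28 = -0.77. At the benign end, power on change is 53% against 66% at 90% symptomatic. At 95% it is 61% against 67%, with differences of -1.21 and -1.26.

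**4. What baseline adjustment does.** At 60% symptomatic, adjusted power is 55% in all women and 56% in the symptomatic subset. Adjustment therefore recovers the power without excluding anyone. It does not change the all-women average.

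**5. New onset.** Giving symptom-free women the same effect and noise, floored at 0, the 60% case has an all-women difference of -0.99 and power of 31% on change. Adjusted power is then 71% in all women against 56% in the subset.

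**6. The non-parametric fallback.** In a three-arm simulation (25 per arm, effect 0.8 SD in one arm, symptomatic controls improving by 1.5 SD, symptom-free change exactly 0), one-way ANOVA on change fell from 84% power with all symptomatic to 39% at q = 0.7 and 21% at q = 0.5. Kruskal-Wallis fell from 82% to 31% and 12%, because of tied zero changes. The fallback does not repair the problem.

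**The case against.** The strongest reply is that no passage says any recruited woman scored zero on any symptom. The Methods section refers to eligible participants, so fuller criteria may exist than this short document lists. If nearly all women had each symptom, little is lost. This stands: the mechanism is shown, its size is not.

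A reader might infer that the intention-to-treat result is biased. It is not. It validly estimates the average effect in the women recruited. The effect in women who have the symptom is a different quantity, so a shortfall of about 40% is not a property of the trial. It follows from assuming 60% symptomatic and no new onset (1 − 0.6 = 0.4).

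A reader might also infer that restricting the analysis is the way to regain power. Steps 4 and 5 show otherwise: most of the loss comes from leaving baseline out, and restriction can cost power when new onset occurs. Nor do symptom-free women always add variance. At 40% symptomatic, the SD of change is 1.90 in all women and 1.99 in the subset.

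The subset has limits of its own. A cut above zero keeps women with very low scores: if the low group averages 1 instead of 0, it removes nobody. No scale is given for hardness, so zero may not mean absent. The trial ran from May 2021 to April 2023 and the analysis is described in the past tense, so a subset added now may be post hoc. With three arm pairs and two follow-up visits, four symptoms would add 4 × 2 × 3 = 24 contrasts.

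What survives the reply is that the plan states no baseline adjustment and no display of who had each symptom, so a reader of the results could not judge how much dilution occurred.

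**Conclusion.** The concern holds in a conditional form. Entry is non-specific, each symptom is compared as unadjusted change in everyone, and any woman at the floor for a symptom cannot show relief of it. To that extent the all-women difference is smaller than the effect in women who have the symptom, and the unadjusted analysis loses power.

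The size cannot be fixed from the documents. Under the assumptions shown, it runs from slight at 95% symptomatic (power 61% against 67%) to large at 40% (13% against 33%), and it is smaller if symptom-free women develop symptoms that treatment prevents. The documents do not support calling the all-women result wrong, quoting a fixed percentage of understatement, or resting statements about relief on the symptomatic subset alone.

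**What to change.** - Keep the all-randomised comparison as the main analysis, but adjust each follow-up symptom score for its own baseline value.
- For breast pain, nipple pain and engorgement, add a supplementary baseline-adjusted arm comparison at each follow-up visit in women whose baseline score for that symptom was above zero. The subset is defined before treatment, so the comparison within it is still randomised.
- Include hardness only if its scale has a baseline value that means absent.
- Report by arm the number with each symptom at baseline and, in the remaining women, new onset (n, %).
- Present the subset results beside the all-women results, not in place of them. Label them post hoc if they were added after the data were seen.

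The cost is revised analysis wording and a few tables from data already collected. The downside is fewer women in each supplementary comparison and more contrasts: 3 symptoms × 2 visits × 3 arm pairs = 18 without hardness. They should therefore be read as supportive.

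### Does last observation carried forward put an early milk volume in place of a zero at 3 months for women who have stopped lactating?

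*Combined protocol and SAP*

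**What the plan says.** The Methods section of the combined protocol and SAP describes entry in these terms: "Postpartum lactating women aged from 21 to 45 with breast symptoms were recruited". Women in the ultrasound arm "participated in four one-hour treatment sessions with the physical therapist over one week". On the last two of its outcomes and the schedule, it states that "breastfeeding self-efficacy, and milk volume were assessed at baseline, immediately post-intervention, and at 3 months following baseline". It gives no method, unit or collection period for milk volume. Lactation or feeding status is not among the listed outcomes.

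The Statistical analysis plan section sets the analysis population with "The data were analyzed using intention-to-treat principles" and handles gaps with "The last observation carried forward imputation was used for imputing missing data". No outcome, and no reason for a value being absent, is treated differently. The main comparison is given as "Repeated measures analysis of variance with Bonferroni post hoc comparisons was used to compare changes in outcome variables between groups", with rank-based tests as the fallback for non-normal data.

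Neither section says what is entered at 3 months for a woman who no longer produces milk.

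**The concern.** For most outcomes a blank means that the value is unknown. Milk volume is different: once lactation has stopped, the value is 0 by definition. If such women were left blank, the carried-forward rule would give them a volume recorded while they were still lactating. The only values available are the post-intervention one, from about week 1 because treatment lasted one week, and the baseline one.

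The 3-month visit is the only follow-up after the immediate assessment, and the Introduction names medium-term effectiveness as an aim. Treatment might also affect whether a woman keeps lactating. The rule could then hide a difference between arms in 3-month volume, or create one. The Introduction itself says that the symptoms can bring exclusive breastfeeding to an early end, so disrupted feeding was on the authors' minds. A similar but weaker worry applies to self-efficacy: a score carried past the end of breastfeeding is not a score observed at 3 months.

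**Working it through.** The plan has no figure to reproduce: the documents give no milk volume, stopping rate, dropout rate or sample size. Two checks are possible.

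**1. What the mechanism would do if it operated**

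For one arm, let V be the 3-month volume in continuing women, w the share who stopped, L the volume carried forward, and b the share of stopped women whose field was left blank.

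- Mean with stopped women at 0: V(1 − w)
- Mean under the rule: V(1 − w) + bLw
- Overstatement in one arm: bLw
- Error in the difference between two arms: b₁L₁w₁ − b₂L₂w₂

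All inputs below are assumptions. V = 700 in both arms, and b = 1 unless stated.

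| Stopped | Carried forward | Mean, arm 1 | Mean, arm 2 | Difference under the rule | True difference |
|---|---|---|---|---|---|
| 20% v 40% | 450 in both | 560 + 90 = 650 | 420 + 180 = 600 | 50 | 140 |
| 20% v 40% | 450 in both, b = 0.5 | 560 + 45 = 605 | 420 + 90 = 510 | 95 | 140 |
| 20% v 40% | 600 v 100 | 560 + 120 = 680 | 420 + 40 = 460 | 220 | 140 |
| 20% v 40% | 100 v 600 | 560 + 20 = 580 | 420 + 240 = 660 | −80 | 140 |
| 20% v 40% | 600 v 300 | 560 + 120 = 680 | 420 + 120 = 540 | 140 | 140 |
| 5% v 10% | 450 in both | 665 + 22.5 = 687.5 | 630 + 45 = 675 | 12.5 | 35 |
| 30% v 30% | 450 in both | 490 + 135 = 625 | 490 + 135 = 625 | 0 | 0 |
| Any | Any, b = 0 | no overstatement | no overstatement | equals the true difference | as given |

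The difference can shrink, grow, reverse or stay the same. The growing and reversing rows need a six-fold gap in carried-forward volume between randomised arms, which nothing in the documents supports. The last row matters most: with b = 0 every error vanishes, whatever the other inputs.

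**2. Whether the documents point to blanks (b above 0)**

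- The imputation sentence is limited to missing data. It does not reach a value that was observed.
- The Methods section says that milk volume was assessed at 3 months. A woman seen at that visit who produces no milk has been assessed, and her result is 0. That is the natural entry.
- No sentence says or implies that such a woman was entered as blank or not applicable.
- The nearest text, in the Introduction, concerns the end of exclusive breastfeeding. A woman who moves to mixed feeding has not stopped lactating.
- Lactation status is not a listed outcome. A woman who missed the visit therefore has an unknown volume, not a known 0. Carrying a value forward for her is the ordinary use of the rule, and its general weaknesses are a separate matter.

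The error therefore needs a blank-field convention that the documents do not show.

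**The case for a change.** The strongest case for acting is that the rule is written without exception, that the recording convention is nowhere stated, and that a reader cannot tell whether a given 3-month volume was observed, zero or carried forward. One sentence would settle it, at little cost. All of that is true, and the conditional arithmetic reproduces.

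What stands is a missing detail. It is fair to ask, when reading the results, how stopped lactation was coded and how many women it concerned in each arm. It does not stand as a fault in the analysis, because the fault appears only under a convention that nobody has shown was used.

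The remedies that might be proposed also bring less than they seem to:

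- Recoding blanks to 0 needs a record of lactation status, which the documents do not list as collected.
- Setting women of unknown status to 0 and then to their carried-forward value would not bound the result. In the illustration a continuing woman is at 700, above both 0 and 450. Giving every arm the same assignment also does not bound the difference between arms.
- A special test is not needed. Zeros leave change from baseline defined, as minus the baseline value. If they make the data non-normal, the plan already provides for it: "Friedman test and Kruskal Wallis test) were used if data were not normally distributed".

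The self-efficacy point is true of any carried-forward score and adds nothing specific to stopped lactation.

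**Conclusion.** No change to the plan follows. The gap is an unstated recording convention that a sensible analyst fills by entering 0 for a woman assessed and found to produce no milk; the imputation rule then does not apply to her. On that reading the error is nil. If blanks were used, the error in an arm difference is b₁L₁w₁ − b₂L₂w₂, and its direction and size cannot be known from the documents. The shift from 140 to 50 shows only what the mechanism can do under assumed inputs.

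The conclusion assumes that the 3-month assessment was recorded as the Methods section describes it, with an absence of milk counted as a result. It would change if the trial records showed that stopped women had been left blank. The matter concerns one of several outcomes, none named as primary. The text reports a finished trial, "A randomized controlled trial was conducted from May 2021 to April 2023", with its analyses in the past tense, so what remains is a question for whoever reads the milk-volume results.

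### Does timing the short-term visit from the end of the intervention leave usual care without a comparable visit?

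*Combined protocol and SAP*

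**What the plan says.** The Methods section gives a single schedule, without distinguishing between arms: the outcomes "were assessed at baseline, immediately post-intervention, and at 3 months following baseline". The sentence after it uses the same two follow-up points for safety and acceptability: "The acceptability of the intervention program and adverse events were recorded immediately post-intervention and at 3 months following baseline".

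The arms are described as follows.

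- **Ultrasound:** women "participated in four one-hour treatment sessions with the physical therapist over one week".
- **Sham:** women "received the same education and breast massage sessions as described above", plus ultrasound at zero intensity.
- **Usual care:** women "received usual obstetric care, which included verbal advice/printed patient information regarding mastitis and breastfeeding" from clinical staff. No sessions, duration or end are stated.

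The Introduction sets the comparison "versus usual obstetric care and sham ultrasound treatment on patient-centered outcomes in the short- and medium-term" as an aim. The Statistical analysis plan section names repeated measures analysis of variance with Bonferroni post hoc comparisons, rank-based alternatives for non-normal data, and last observation carried forward for missing values. It mentions neither visit windows nor the actual day of assessment.

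**The concern.** The schedule runs on two clocks. The later visit is counted from baseline, which every woman has. The middle visit is counted from the end of an intervention, and only two of the three arms have a described end. Read literally, the middle visit has no defined date in usual care.

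This could matter for two reasons. First, breast symptoms may change over days whatever the allocation. If usual care were assessed systematically earlier or later than the other arms, the short-term contrast would contain some of that change, and an analysis that treats the visit as one common level would neither reveal nor correct it. Second, the middle visit is the only one that can serve the short-term half of the stated aim. The first adverse-event recording shares the anchor, so the length of its reporting period in usual care is also unstated.

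**Working it through.** The documents state no figure on this point, so there is none to reproduce. The check sets the Methods text for each arm against the schedule.

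| Arm | Described course | End of course defined? | Short-term visit placed by the text? | 3-month visit placed by the text? |
|---|---|---|---|---|
| Ultrasound | four sessions in one week | yes | yes | yes, from baseline |
| Sham | same education and massage sessions | yes, by reference to the ultrasound arm | yes | yes, from baseline |
| Usual care | advice or printed information among its contents | no | not explicitly | yes, from baseline |

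**Step 1: what is missing.** One entry is undefined: the day of the short-term visit in usual care. The interval from baseline to the first session is not given either, so the exact day from baseline is approximate in the treated arms too.

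**Step 2: how the gap would be filled.** The text gives one schedule for all outcomes and one programme length. A coordinator placing the usual-care visit has only one figure to work from, the one-week treatment period. Assessing all arms at about one week is the obvious reading, and nothing in the documents points to another.

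**Step 3: what a mismatch would do.** Suppose symptoms change by *r* standard deviations per day regardless of treatment, and the usual-care visit falls *d* days away from the visit in the other arms. The contrast with usual care then shifts by

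shift = *r* × *d*.

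Neither input is in the documents. As a pure assumption, take *r* from 0.05 to 0.20 SD per day.

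- *d* = 0: shift = 0 for every *r*.
- *d* = 1, *r* = 0.05: 0.05 × 1 = 0.05 SD.
- *d* = 5, *r* = 0.20: 0.20 × 5 = 1.0 SD.

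This range is not evidence of size. It shows that the point turns on *d*, and the natural reading puts *d* near zero.

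**Step 4: where it could reach.** Ultrasound versus sham is free of the anchor mismatch, because both arms have the same sessions. Observed 3-month values are timed from baseline throughout; a missing 3-month value filled by last observation carried forward would bring in the short-term one. An overall group-by-time test, or a group comparison averaged over visits, also includes the short-term visit. The plan does not say at which level its post hoc comparisons are made, so a count of affected comparisons would be guesswork.

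**Step 5: adverse events.** The second recording is at the same time from baseline in every arm, so total follow-up is common. Only the dividing point between the first and second periods is unstated in usual care. Acceptability of the programme chiefly concerns the women who had one.

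**The case for a change.** The strongest case for acting is that a reader cannot tell from the text whether the short-term contrast with usual care compares women at equal time since baseline. That contrast is a stated aim, the planned analysis would not expose unequal days, and a baseline anchor was available because the same sentence uses one for the later visit. If the days were equal, a short table would settle the matter at almost no cost.

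Most of this stands as a comment on reporting. It does not show a fault in the design. An unstated day is not evidence of a mistimed one, and the trial, described as run from May 2021 to April 2023, can no longer change its schedule. An analysis adjusting for actual day would be no clear improvement, because assessment day is set after randomisation and conditioning on it can itself introduce bias.

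A related worry is that treated women may be measured just after a hands-on session, so that a short-term difference reflects a passing response. The Introduction does say that "only low-level evidence has shown positive effects of breast massage, a physical technique, on pain, milk supply and symptom relief", but it gives no duration for such a response. The wording can equally mean the end of the programme rather than minutes after a session. Even on the narrower reading, the response is a genuine effect of the allocated treatment and is what a short-term comparison measures. The documents nowhere present the short-term result as lasting benefit, and the 3-month visit is there to address durability.

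**Conclusion.** The gap is real but small: the plan does not state the day of the short-term visit in usual care. It is a missing detail that investigators would sensibly fill with the end of the one-week treatment period, and on that basis the short-term comparison remains sound. No stated rule or figure is wrong, and nothing in the analysis plan needs correcting.

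The size of any timing effect is unknown and may be zero. The conclusion rests on one assumption that the documents neither confirm nor contradict: that usual-care women were assessed at about one week, as in the other arms. If the assessment days proved to differ materially, the short-term contrasts with usual care would need more cautious reading, while ultrasound versus sham would still have no anchor mismatch. A good trial report would give the actual days from baseline to the short-term assessment by arm, or say that dates were not recorded. That is ordinary reporting practice and requires no change to the plan.

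### Adverse events have only two documented recording times, after the four-session week and at 3 months, so short-lived in-course events rest on recall and go unrecorded in women who miss both

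*Combined protocol and SAP*

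**What the plan says.** The Methods give two times for harms: "adverse events were recorded immediately post-intervention and at 3 months following baseline". The ultrasound course is "four one-hour treatment sessions with the physical therapist over one week". Women in the sham arm "received the same education and breast massage sessions as described above", with sham ultrasound added, so the same schedule governs both therapist arms. Women in the third arm "received usual obstetric care, which included verbal advice/printed patient information regarding mastitis and breastfeeding from the medical or nursing staff"; no therapist sessions are described for them.

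The efficacy outcomes "were assessed at baseline, immediately post-intervention, and at 3 months following baseline". The same post-intervention label is thus the single middle time point for efficacy and the first time point for harms.

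The Statistical analysis plan section has two rules that bear on women who leave: "The data were analyzed using intention-to-treat principles" and "The last observation carried forward imputation was used for imputing missing data". It gives no rule for analysing adverse events. Neither section describes a session-level check, a diary, a spontaneous-reporting route, a withdrawal visit, or follow-up of women who stop.

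**The concern.** Massage, with active or sham ultrasound, is given to women who already have breast symptoms, in several visits over a few days. A flare after the first or second visit is the kind of event that a safety record should catch, and the therapist sees the woman again within days. As documented, the first recording time comes only when the course is over.

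Two losses follow. An event that has resolved by then depends on the woman's memory. And a woman who finds the treatment hard to tolerate may be the one who does not come back. If poor tolerability leads to missed assessments, the events removed from the record are those that matter most for judging acceptability. At stake are the absolute adverse-event rates in the two therapist arms and, possibly, the ultrasound versus sham contrast, which is the one that isolates ultrasound.

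**Working it through.** The documents state no adverse-event rate, dropout rate or sample size, so there is no plan figure to reproduce. The first part is a reading of the schedule; the second is an illustration on assumed rates.

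**1. What the first time point means.** The post-intervention label could in principle mean after each session. For the efficacy outcomes it is a single assessment between baseline and 3 months, and the harms sentence uses the same label. The natural reading is one assessment after the week of treatment.

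**2. Delay from event to first planned record, for a transient event after session 1.**

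| Woman's path | First planned record | Delay |
|---|---|---|
| Attends the end-of-course assessment | End of course | Up to about 1 week |
| Misses it, attends at 3 months | 3 months after baseline | About 13 − 1 = 12 weeks |
| Misses both | None | Never recorded |

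**3. Whether the missing-data rule helps.** Carrying forward needs an earlier observation of the same variable. Adverse events have no record before the end of the course, so a woman who misses that assessment has nothing to carry forward. Intention-to-treat keeps her in the denominator but cannot supply an event that was not recorded.

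**4. Illustration.** Assumptions, none from the documents: true risks of 20% (ultrasound) and 10% (sham); a fraction *f* of affected women miss both assessments; no unaffected woman is lost. Per 100 women with true risk *p*%, the recorded rate among those assessed is

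*p*(1 − *f*) / (100 − *pf*).

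| *f* ultrasound / sham | Ultrasound | Sham | Difference (points) | Ratio |
|---|---|---|---|---|
| 0 / 0 (truth) | 20.0% | 10.0% | 10.0 | 2.00 |
| 1/2 / 1/2 | 10/90 = 11.1% | 5/95 = 5.3% | 5.8 | 2.11 |
| 1/4 / 1/4 | 15/95 = 15.8% | 7.5/97.5 = 7.7% | 8.1 | 2.05 |
| 1/2 / 1/4 | 10/90 = 11.1% | 7.5/97.5 = 7.7% | 3.4 | 1.44 |
| 1/4 / 1/2 | 15/95 = 15.8% | 5/95 = 5.3% | 10.5 | 3.00 |

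With all randomised women in the denominator and half of affected women lost in each arm, the rates are 10/100 and 5/100: difference 5 points, ratio 2.00.

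Equal proportional loss lowers both rates and the difference but leaves the ratio near 2. Heavier loss under ultrasound shrinks both measures; heavier loss under sham enlarges both. In these cases the absolute rates are always understated where loss occurs, while the direction of the contrast depends on inputs that the documents do not give.

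**The case against.** The strongest reply is that silence is not evidence of absence. The Methods are a short summary in the past tense; therapists may have kept session notes or noted complaints as they arose. That stands: the finding is that no in-course recording is documented, not that none took place.

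Second, recall is short for most women. Completers are asked within about a week, and harm that persists can be observed directly at the end-of-course assessment, when breast and nipple pain, engorgement, hardness and temperature are also measured. That stands too, and it limits the recall problem to transient events.

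Third, stopping treatment is not the same as missing assessments. Under intention-to-treat a woman who stopped attending sessions could still have been assessed. This is right; an event is lost for certain only if she misses both assessments. But no procedure for following such women is described.

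A reader might infer that ultrasound would look safer against sham than it is. The documents do not support that. Both therapist arms have the same recording times, nothing shows more treatment-limiting events or heavier loss under ultrasound, and under equal proportional loss the illustrative ratio does not shrink.

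Finally, the aims concern effectiveness, no adverse-event test is planned, and recruitment and follow-up are described as finished. That limits what can now be changed, but adverse events are a listed measurement and their rates will be read as a description of tolerability.

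**Conclusion.** The gap is real and worth acting on. Followed as written, the schedule can miss transient events after early sessions and any in-course event in women who miss both assessments, and the missing-data rule cannot repair this. Absolute adverse-event rates in the ultrasound and sham arms may therefore be understated.

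The size is unknown. The fall in the risk difference from 10 points to 5.8 or 8.1 rests wholly on assumed risks, assumed loss confined to affected women, and no recovery of lost events at 3 months. Any distortion of ultrasound versus sham is conditional on differences in event and loss rates that the documents do not report, so no direction should be claimed. The conclusion also rests on reading the first recording time as one assessment after the whole course. Confidence is moderate.

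**What to change.** For a plan of this design:

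- Record adverse events with the same short checklist at every existing session, in both therapist arms.
- Contact any woman who stops early, briefly and at the time she stops, and ask her reason and whether she had any event.
- Report session-level events for ultrasound versus sham only, because usual care has no sessions described. Keep the two existing time points for the three-arm comparison, so that more frequent questioning does not by itself raise the counts in the therapist arms.
- Report early stoppers by arm, with reasons.

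The cost is one checklist at visits that already take place, plus a small contact effort outside scheduled visits for women who stop. More minor events will be counted in the two therapist arms than under the present schedule.

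The Methods describe the trial as conducted from May 2021 to April 2023, so collection cannot be changed. At minimum, the report should say how in-course events were captured, use any session notes that exist, say how women who stopped were followed, and state the two-time-point recording as a limitation.
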